5.1.5 On-treatment assessments

- Incidence of protocol violations
- Incidence of adverse reactions
- SOFA scores and constituents
- APACHE II/IV score and constituents

5.1.6 Hospital discharge assessment

- Organ-failure-free days at 28 days
- Vital status at hospital discharge
- Discharge destination (home, home with services, SNF, rehab, LTACH)

5.1.7 Management of blood samples

- Troponin will be tested in the Intermountain clinical laboratory
- Vascular biomarkers will be tested in [name] laboratory at BIDMC. Locally at IMC, they will be centrifuged and stored at -80C before transportation on dry ice.

5.2 Esmolol infusion

The esmolol infusion will be managed as per the protocol in APPENDIX 1. Esmolol will be stopped and cannot be restarted without explicit investigator approval for STOP events. Further needs for volume expansion will be assessed on the basis of VOLUME EXPANSION events. If the patient is taken to the operating room, esmolol

infusion will be stopped when the patient leaves the ICU for the OR and will only be resumed after reevaluation of cardiac index and adequacy of volume expansion, given the possibility of changes in volume status and degree of shock during surgery.

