2.0 Study Summary

2.1 **Title:** Esmolol to Control Adrenergic Storm in Septic Shock (ECASSS) – ROLL-IN

2.2 **Objective:** To evaluate the adequacy and efficiency of study protocols for the main ECASSS study.

2.4 **Study design:** Prospective, single arm, feasibility (“roll-in”) study of esmolol infusion in septic shock.

1. **Inclusions.** We will include patients admitted to the ICU for sepsis who are within 48 hours of septic shock and ICU admission and are simultaneously tachycardic (heart rate >90/min) **and** on vasopressors for > 60 min. Patients must meet criteria at the time of enrollment.
2. **Final safety check.** After enrollment and before esmolol infusion, ScvO₂, transthoracic echocardiogram, evaluation of fluid responsiveness, and review of telemetry/EKGs will occur to assure that no exclusion criteria are present.
 - a. If no exclusion criteria are present, patients will start esmolol infusion
 - b. If patient is still fluid responsive but otherwise has no exclusions, fluid will be administered by explicit protocol until no longer fluid responsive, and then the patient will receive esmolol infusion. If tachycardia has resolved as a result of volume expansion, esmolol infusion will not occur until tachycardia and vasopressor administration co-occur. After esmolol infusion, volume expansion will be managed as part of the esmolol titration protocol.
 - c. Patients who fail the final safety check will NOT start esmolol infusion but will be followed for non-interventional aims (e.g., serial TTEs, vascular biomarkers) to understand better the natural history of cardiogenic shock superimposed on septic shock.
3. **Esmolol infusion**
 - a. Esmolol infusion, started without bolus, with slow upward titration to a maximum infusion rate is protocolized (see protocol in Appendix 1), with a target heart rate of 80-90/min.
 - b. Esmolol infusion will be stopped in the event that cardiogenic shock, excessive bradycardia, grade 2 or grade 3 heart block, or hypotension, or bronchospasm occur, as per protocol.
4. **Other care**
 - a. ICU patients are managed according to current Surviving Sepsis campaign guidelines as per usual practice.

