2.6 Exclusion criteria

1. Lack of informed consent.
2. Currently receiving ECMO.
3. Known pregnancy or nursing.
4. Patient is a prisoner.
5. Patient on hospice (or equivalent comfort care approach) at or before the time of enrollment.
6. Known or current atrial fibrillation.
7. Previously enrolled in the trial.
8. Known allergy to esmolol or vehicle (see Appendix 2 for BREVIBLOC vehicle ingredients).
9. Receipt of nodal blocking agents (see Appendix 3 for list of such agents) within three half lives
10. Hemoglobin $<$ 7 gm/dl.
11. Cardiac arrest within 24 hours.
12. Pulmonary hypertension (moderate or severe), from documented history of prior right heart catheterization or current evidence on TTE of **any** of the following
 - mPAP \geq 35mmHg

- SPAP \geq 60mmHg
13. Cardiovascular collapse, as manifested by inability to achieve a MAP of 65 mmHg with vasopressor therapy.
 14. Cardiogenic shock, as defined by **any** of the following
 - Cardiac index \leq 2 L/min/m²
 - Ejection fraction \leq 25%
 - ScvO₂ \leq 60%
 - Current infusion of any dose of dobutamine, milrinone, or dopamine
 - Current infusion of epinephrine for clinically diagnosed cardiogenic shock
 15. Significant atrioventricular dysfunction
 - Sick sinus syndrome
 - PR interval > 200 msec
 - Current evidence or prior history of Grade 2 or Grade 3 heart block
 - Pacemaker or plans to place a pacemaker
 16. Pheochromocytoma or status asthmaticus
 17. Receiving clonidine, guanfacine, or moxonidine
 18. Hemoglobin < 7 gm/dl
 19. Cardiovascular collapse (failure to achieve MAP of 65mmHg)
 20. Cardiac arrest within 24 hours
 21. Worse than moderate aortic stenosis
 - Known aortic stenosis, with any of (1) mean gradient \geq 40 mmHg OR (2) maximum gradient \geq 60mmHg OR (3) aortic valve area \leq 1.0cm² OR (4) aortic valve area index \leq 0.85cm²/m² body surface area.
 22. Worse than mild mitral stenosis
 - Known mitral stenosis, with any of (1) valve area \leq 1.5 cm² OR mean gradient \geq 5 mmHg.

2.7 Sample size: The study will enroll up to 10 patients at 1 center.

2.8 Non-clinical outcomes for ROLL-IN:

1. Proportion of eligible patients consented
2. Proportion of compliance with final safety check
 - a. Protocol compliance is considered adequate where compliance is 100% for the safety check.
3. Proportion of protocol compliance

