5.1.1.2 Evaluation for cardiogenic shock

If cardiogenic shock is documented at this point, a subject will be followed for outcomes and biomarkers but esmolol will not be administered. This step involves evaluation of LV ejection fraction, measurement of ScvO₂, and direct measurement of cardiac index using the NICOM bioreactance device.

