8.0 Risk Assessment

8.1 Potential Risks

There are potential risks (as well as benefits) to study subjects. Selective β 1-blockade in septic shock has reasonable pilot data in favor of its safety; our observations about improved survival with relative bradycardia also suggest that interventions to induce relative bradycardia will be safe. The primary concerns about risk related to β 1-blockade in septic shock (based on theoretical considerations) are of decreased cardiac output, which is why we will titrate esmolol without bolus doses, starting at very low doses, and we will exclude patients with preexisting or intercurrent cardiogenic shock. After enrollment and before esmolol infusion, we will perform a final verification that cardiogenic shock is not present (using the NICOM™ measurements and initial research echocardiogram). Patients with preexisting conduction system disease may also be at risk for heart block or excessive bradycardia, so they are excluded from this study as well (this will also be verified before esmolol infusion, from the EKG monitors at the patient's bedside).

We have chosen esmolol because it is β 1-selective (thereby decreasing the hypothetical risk of pulmonary effects possible with non-selective β -blockade), because it is available as a continuous infusion (thereby limiting the risk of bolus-associated adverse effects) and because it has a very short half-life (allowing essentially immediate cessation of effect when the infusion is stopped). The theoretical side effects of esmolol infusion would all reverse within minutes of discontinuation of esmolol, and explicit rules will dictate discontinuation of esmolol infusion.

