8.2 Risk abatement strategies

8.2.1 Cardiogenic shock. As indicated above, patients with preexisting cardiogenic shock are excluded from enrollment, and after enrollment a formal evaluation to exclude cardiogenic shock will be performed before esmolol infusion. The esmolol titration protocol incorporates continuous monitoring of cardiac output using the non-invasive NICOM™ device, and in the rare situation that cardiogenic shock should ensue, esmolol titration will be discontinued and appropriate supportive measures will be instituted. Our use of a no-bolus, slow upward titration protocol for the esmolol infusion is specifically designed to avoid this potential complication.

8.2.2 Excessive bradycardia and/or hypotension. As indicated above, patients with preexisting conduction system disease are excluded from enrollment, and a formal evaluation to exclude conduction system disease will be performed before esmolol infusion. In the event that hypotension or excessive bradycardia should ensue during esmolol infusion, esmolol will be discontinued and appropriate supportive measures will

be instituted. Our use of a no-bolus, slow upward titration protocol for the esmolol infusion is specifically designed to avoid this potential complication.

8.2.3 Hypersensitivity reaction. This is extremely rare. Patients with known hypersensitivity to esmolol or vehicle are excluded from the study. Should this occur, esmolol infusion will be stopped and appropriate treatment measures will be instituted. The short half-life of esmolol avoids concerns about treatment of anaphylaxis in patients on β -blockers, should anaphylaxis occur.

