ECASSS ROLL-IN Study Drug Titration protocol

Fundamental rules for study drug titration:

The target heart rate is 85 bpm. Start study drug infusion at 20 mcg/kg/min, without bolus, if HR \geq 100 bpm. If HR >90 bpm and <100 bpm, start study drug infusion at 10 mcg/kg/min, without bolus. Increase by 20 mcg/kg/min every 20 minutes as long as HR > 90 bpm, to a maximum dose of 100 mcg/kg/min. If HR < 80 bpm and > 70 bpm, decrease infusion rate by 10 mcg/kg/min; if HR ≤ 70 bpm and > 60 bpm, decrease infusion rate by 20 mcg/kg/min. Stop study drug infusion whenever a STOP EVENT occurs. Study drug infusion is completed 3 hours after vasopressor infusions have stopped. The up-titrations can be smaller than stipulated if the clinician and/or investigator feels that a small up-titration is indicated. Up-titrations should not occur during a REASSESS VOLUME STATUS event.

Study drug should be preferentially infused centrally; where no port is available, study drug should **not be** infused into a small peripheral vein or via butterfly catheter.

STOP EVENTS:

1. If HR is ever ≤ 60 bpm, immediately stop infusion for 20 minutes, then restart at half the previous infusion rate, rounded to nearest 10 mcg/kg/min. Do not resume infusion until HR > 70 bpm.
2. If vasopressor dose increases by 0.2 mcg/kg/min norepinephrine (or equivalent) AND doubles within 60 min despite adequate volume expansion, STOP the study drug infusion. Alternatively, if the treating clinician believes that the shock is worsening significantly, STOP the study drug infusion. Do not resume without explicit approval of study physician.
3. If cardiogenic shock develops ($ScvO_2 \leq 60\%$ OR LV Ejection Fraction $\leq 25\%$ OR Cardiac Index ≤ 2.0 L/min/m²), STOP the study drug infusion. Do not resume without explicit approval of study physician.
4. If clinically apparent bronchospasm develops, STOP the study drug infusion. Do not resume.
5. If Grade 2 or Grade 3 heart block develops, immediately STOP the study drug infusion. Do not resume.

REASSESS VOLUME STATUS EVENTS:

When markers of potential preload deficit occur (urine output < 0.5 ml/kg/hr OR vasopressor dosage increase), immediately EVALUATE FOR VOLUME RESPONSIVENESS. A vasopressor dosage increase is defined as at least 0.05 mcg/kg/min absolute AND 20% relative increase in the norepinephrine (or equivalent) infusion.

Titrate vasopressors as per local practice to maintain MAP ≥ 65 mmHg. Norepinephrine is the preferred primary vasopressor.

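### After surgery, section 5.2 lets esmolol resume on cardiac index and volume status alone, so an unmeasured ScvO2 of 60% or less would not prevent re-infusion

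*Combined protocol and SAP*

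**What the plan says.** Section 5.2 (Esmolol infusion) covers surgery during treatment. Esmolol stops when the patient leaves the ICU and "will only be resumed after reevaluation of cardiac index and adequacy of volume expansion". The reason given is that surgery may alter volume status and the severity of shock. ScvO2 and LVEF are not mentioned.

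Cardiogenic shock is defined in 2.6 item 14 and again in 4.3.1. Any one of five criteria is enough: cardiac index of 2 L/min/m2 or less, ejection fraction of 25% or less, ScvO2 of 60% or less, "Current infusion of any dose of dobutamine, milrinone, or dopamine", or epinephrine given for clinically diagnosed cardiogenic shock.

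The check before the first infusion is wider than the one in 5.2. Section 5.1.1.2 says: "This step involves evaluation of LV ejection fraction, measurement of ScvO₂, and direct measurement of cardiac index using the NICOM bioreactance device". Section 2.4 item 2 lists ScvO2, an echocardiogram and a fluid-responsiveness evaluation, and adds that "review of telemetry/EKGs will occur to assure that no exclusion criteria are present".

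During infusion, STOP event 3 in Appendix 1 ("If cardiogenic shock develops") is triggered by any one of ScvO2, LVEF or cardiac index at the same thresholds. Section 8.2.1 states: "The esmolol titration protocol incorporates continuous monitoring of cardiac output using the non-invasive NICOM" device.

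**The concern.** Section 5.2 asks for a fresh clearance because shock may have worsened in the operating room, but it tests only one of the measured criteria by which the protocol defines cardiogenic shock. Those criteria are alternatives, so passing on cardiac index does not rule out failing on ScvO2. A patient whom the protocol would have barred from the first infusion could be restarted on a beta-blocker with no breach of 5.2. The stake is the safety of that patient. The roll-in is also meant to test the study procedures before a larger multi-center trial (7.2), so a gap in the restart rule is best closed now.

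**Working it through.** The plan states no figure on this point, so the main check compares the rules. A short illustrative calculation follows.

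**Step 1. Criteria named at each decision.**

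| Criterion (2.6 item 14) | Before first infusion (5.1.1.2) | STOP event 3 | Resumption after surgery (5.2) |
|---|---|---|---|
| Cardiac index ≤2 | yes | yes | yes |
| ScvO2 ≤60% | yes | yes, if measured | no |
| LVEF ≤25% | yes | yes, if measured | no |
| Dobutamine, milrinone or dopamine | under the general check in 2.4 item 2 | not listed | no |
| Epinephrine for cardiogenic shock | under the general check in 2.4 item 2 | not listed | no |

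Of the three measured criteria, 5.2 names one. The two infusion criteria need no measurement, so they carry less weight.

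**Step 2. Does the volume check bring ScvO2 in?** No. The tests in 4.2 are CVP, passive leg raise, fluid challenge and stroke volume variability.

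**Step 3. Is ScvO2 scheduled elsewhere?** No. It is absent from the 24-hour and on-treatment lists (5.1.4, 5.1.5), and the STOP-compliance items in 2.8 item 3b do not name it. STOP event 3 can act only on a value that someone has obtained. Secondary outcome 7 (2.8.2) likewise counts a low ScvO2 only when it is measured. Figure 2 could not be seen, but 5.1.1.1 ties it to the check after enrollment, not to resumption after surgery.

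**Step 4. Can cardiac index exceed 2 with ScvO2 at or below 60%?** By the Fick relation:

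venous saturation = SaO2 − VO2 / (1.34 × Hb × 10 × CI)

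None of the inputs is a trial figure. The assumptions are SaO2 0.97, VO2 of 100, 125 or 150 mL/min/m2, 1.34 mL oxygen per gram of haemoglobin, and mixed venous saturation standing in for ScvO2. Example: Hb 10 g/dL, CI 2.5, VO2 125 gives 0.97 − 125/335 = 0.597.

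| CI | Hb 8 (VO2 100 / 125 / 150) | Hb 10 | Hb 12 |
|---|---|---|---|
| 2.1 | 52.6 / 41.5 / 30.4% | 61.5 / 52.6 / 43.7% | 67.4 / 60.0 / 52.6% |
| 2.5 | 59.7 / 50.4 / 41.0% | 67.1 / 59.7 / 52.2% | 72.1 / 65.9 / 59.7% |
| 3.0 | 65.9 / 58.1 / 50.4% | 72.1 / 65.9 / 59.7% | 76.3 / 71.1 / 65.9% |

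Setting venous saturation to 60% gives CI = VO2 / (1.34 × Hb × 10 × 0.37). At VO2 125 this is 3.15 for Hb 8, 2.52 for Hb 10 and 2.10 for Hb 12. With Hb 10 and VO2 125, changing SaO2 to 0.95 or 0.99 moves it to 2.67 or 2.39.

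Discordance is therefore possible, mainly at low haemoglobin. The protocol admits haemoglobin of 7 g/dL and above, and 5.2 does not ask for a value after surgery. Discordance becomes unlikely at 12 g/dL once cardiac index is above 2.5.

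**The case against.** The strongest reply is that the omission is not peculiar to surgery. ScvO2 is not scheduled at any time after the first infusion starts, and on-treatment surveillance rests on cardiac index: continuous NICOM in 8.2.1 and a 30-minute moving average in 2.8 item 3b. Section 8.1 even describes the pre-infusion verification by NICOM and echocardiogram without mentioning ScvO2. On this view 5.2 simply continues the on-treatment approach. The observation is right, and it limits the point. But resumption after surgery is where the protocol itself demands a new clearance because shock may have changed, and 2.4 and 5.1.1.2 show what clearance otherwise involves.

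There are also safeguards that do not depend on ScvO2. STOP event 2 halts esmolol if the norepinephrine-equivalent dose rises by 0.2 mcg/kg/min and doubles within 60 minutes despite adequate volume, or if the clinician judges shock to be significantly worse. Low urine output or a smaller vasopressor rise triggers a volume assessment and blocks up-titration. These would catch some deteriorating patients once infusion resumes, but they do not guarantee detection of a silent low ScvO2. NICOM follows the criterion already re-checked. The approval rule in 5.2 attaches to STOP events, and leaving for the operating room is not one of the five listed.

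Two stronger readings are tempting. A reader might infer that the protocol allows esmolol in known cardiogenic shock. It does not: a measured ScvO2 of 60% or less triggers STOP event 3, and 5.2 sets minimum conditions without discouraging the draw. A reader might also infer that an inotrope started in the operating room would be ignored. It would be visible at the bedside, 2.4 item 3b says "Esmolol infusion will be stopped in the event that cardiogenic shock" occurs, and 8.1 says "we will exclude patients with preexisting or intercurrent cardiogenic shock". What remains there is a lesser wording gap, because neither 5.2 nor STOP event 3 lists those infusions.

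**Conclusion.** The point holds in a narrow form. Section 5.2 as written can be satisfied by a patient with cardiac index above 2, adequate volume and an unmeasured ScvO2 of 60% or less, a state that the protocol defines as cardiogenic shock. This rests on the wording alone. The Fick figures show only that such a patient can exist, under assumed oxygen consumption and saturation.

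No frequency can be given, because the documents report neither how often surgery interrupts infusion nor how often low ScvO2 accompanies an acceptable cardiac index. Exposure is at most 10 patients at one center and could be none. Titration is slow and without bolus, the drug wears off quickly, and the safety committee reviews at 3 and 6 patients, although it cannot see a value that was never measured. This is an inexpensive improvement to consider and does not call the study's conduct into question.

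**What to change.** Amend 5.2 so that, after return to the ICU, resumption requires all of the following:

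- cardiac index above 2.0 L/min/m2;
- ScvO2 above 60%, drawn from the central venous catheter already required at inclusion (2.5 item 3);
- none of the infusions in 2.6 item 14 running (dobutamine, milrinone or dopamine at any dose, or epinephrine for clinically diagnosed cardiogenic shock);
- adequate volume expansion by one of the tests in 4.2;
- LVEF above 25% on any echocardiogram already done since surgery.

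A repeat echocardiogram need not be mandated. An unmeasured low LVEF then remains a residual gap, which the protocol should acknowledge.

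STOP event 3 can stay as it is. The post-surgery checks should not be counted in the safety-check compliance outcome (2.8 item 2). Its adequacy threshold is 100%, so one late draw at a resumption could make a feasibility outcome fail.

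The cost is one amended sentence and a few case report form fields. Each resumption adds one ScvO2 draw, a look at the running infusions and possibly a short delay.

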6.0 Data Collection and Safety Monitoring

6.1 Data Collection and Data Quality Monitoring

Research coordinators and/or investigators will collect data and record them on paper or electronic CRFs. Data will be analyzed internally. Data quality will be reviewed using front-end range and logic checks at the time of data entry and back-end monitoring of data. Patient records and case report forms will be examined on a random spot check basis to evaluate the accuracy of the data entered into the database and monitor for protocol compliance.

6.2 Safety Monitoring

The safety of this feasibility “roll-in” study will be monitored by a three-member safety monitoring committee (SMC). The SMC will have full access to all study data (including a narrative account of each patient’s course) and will review for any major adverse events at 3 patients enrolled and at 6 patients enrolled. While septic shock is a high-mortality condition at baseline, every death during esmolol infusion will be reported (including narrative account and full study data) within 24 hours to the chair of the SMC by the study PI. Further details of safety monitoring and reporting are given at Appendix 4.

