10.2 SERIOUS ADVERSE EVENTS

Serious adverse event collection begins after the patient or LAR has signed informed consent and has received study drug or undergone study procedures. If a patient experiences a serious adverse event after consent, but prior to receiving study drug, the event will NOT be collected unless the investigator feels the event may have been caused by a study procedure.

Investigators must alert the chair of the SMC of any **serious and study drug or study procedure related** adverse event within 24 hours of investigator awareness of the event. Alerts issued via telephone are to be immediately followed with official notification on the adverse event case report form. See Appendix 4 for reporting timelines for serious, unexpected, study related events (SAEs) and serious, unexpected suspected adverse reactions (SUSARs).

As per federal definitions (primarily in 21 CFR 312.32(a)), a **serious** adverse event is any adverse event that results in one of the following outcomes:

- Death
- A life-threatening event, one that places the subject at immediate risk of death (this does not include an event that, had it been more serious, would have placed the subject at immediate risk of death)
- Prolonged inpatient hospitalization or rehospitalization
- Persistent or significant disability/incapacity, indicating a substantial disruption of a person's ability to conduct normal life functions (i.e., the adverse event resulted in a significant, persistent or permanent change, impairment, damage or disruption in the patient's body function/structure, physical activities and/or quality of life).

Important medical events that may not result in death, be life-threatening, or require hospitalization may be considered serious adverse events when, based upon appropriate medical judgment, they may jeopardize the patient and may require medical or surgical intervention to prevent one of the outcomes listed in this definition.

Given the short-acting nature of esmolol and the limited duration of the study infusion, surveillance for adverse events will extend through 24 hours after completion of the esmolol infusion. Serious adverse events will be collected during and for 24 hours after the esmolol infusion, regardless of the investigator's opinion of causation. Thereafter, serious adverse events are not required to be reported unless the investigator feels the events were related to study drug or a protocol procedure.

APPENDIX 1

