Investigators will grade the strength of the relationship of an adverse event to esmolol or study procedures as follows:

- **Definitely Related:** The event follows: (a) a reasonable, temporal sequence from study drug or a study procedure; and (b) cannot be explained by the known characteristics of the patient’s clinical state or other therapies; and (c) evaluation of the patient’s clinical state indicates to the investigator that the experience is definitely related to study procedures.
- **Probably or Possibly Related:** The event should be assessed following the same criteria for “Definitely Related”. If in the investigator’s opinion at least one or more of the criteria are not present, then “probably” or “possibly” associated should be selected.

- Probably Not Related: The event occurred while the patient was receiving esmolol or undergoing study procedures but can reasonably be explained by the known characteristics of the patient's clinical state or other therapies.
- Definitely Not Related: The event is definitely produced by the patient's clinical state or by other therapies administered to the patient.
- Uncertain Relationship: The event does not meet any of the criteria previously outlined.

Certain serious adverse events will not require adjudication; they will always be understood to be drug-related.

[figure not shown]
- Third-degree heart block while receiving esmolol infusion.

A4.3. CLINICAL OUTCOMES THAT MAY BE EXEMPT FROM ADVERSE EVENT REPORTING

Study-specific clinical outcomes of septic shock, as outlined in Sections 2.8 and 3.5 (Primary and Secondary Outcomes) and Section 5.1 (Assessments) are exempt from adverse event reporting unless the investigator deems the event to be related to the administration of study drug or the conduct of study procedures (or of uncertain relationship). The following are examples of events that will be considered study-specific clinical outcomes

- Death not related to the study drug or procedures.
- Cardiovascular events: changes in doses of vasoactive drugs or VOLUME EXPANSION events.
- Organ dysfunction events: changes in the SOFA score and its constituents.
- Cardiogenic shock that does not resolve 20 minutes after cessation of esmolol

A4.4. DECISION TREE FOR REPORTING ADVERSE EVENTS

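### Section 6.2's all-cause 24-hour death report to the SMC chair ends when esmolol stops, so a death soon after a STOP event that is judged unrelated has no guaranteed 24-hour notice in the visible text

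*Combined protocol and SAP*

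**What the plan says.** Section 6.2 sets up a three-member SMC, with reviews at 3 and at 6 patients enrolled. It adds that "every death during esmolol infusion will be reported (including narrative account and full study data) within 24 hours to the chair of the SMC". The sentence first acknowledges the high background mortality of septic shock and attaches no relatedness condition.

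Several other places govern when the infusion ends and how a death is handled:

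- **Section 2.4:** "Esmolol infusion will be stopped in the event that cardiogenic shock, excessive bradycardia, grade 2 or grade 3 heart block, or hypotension, or bronchospasm occur".
- **Appendix 1, STOP event 2:** the infusion stops on a rapid vasopressor rise. Also, "Alternatively, if the treating clinician believes that the shock is worsening significantly, STOP the study drug infusion".
- **Appendix 1, STOP events 2 and 3:** "STOP the study drug infusion. Do not resume without explicit approval of study physician". Bronchospasm and Grade 2 or 3 heart block end the infusion for good.
- **Appendix 1, STOP event 1 (heart rate 60 or below):** "immediately stop infusion for 20 minutes, then restart at half the previous infusion rate", once heart rate has recovered above 70.
- **Section 10.2:** "Serious adverse events will be collected during and for 24 hours after the esmolol infusion", whatever the investigator thinks of causation. The 24-hour alert to the SMC chair, however, is for serious events attributed to the drug or a study procedure.
- **Appendix 4, A4.3:** outcomes exempt from adverse event reporting include "Death not related to the study drug or procedures".

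**The concern.** The 6.2 rule is the one 24-hour death report in the visible text that does not depend on someone's view of cause. That matters here because the study is small and has no control arm. An excess of deaths cannot be seen by comparison, so prompt review of individual cases carries most of the safety oversight.

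The rule's window closes when the drug is stopped, and the protocol stops the drug in patients who are deteriorating. Section 2.8 treats only 100% compliance with STOP events as adequate. Good adherence to the titration protocol therefore moves deteriorating patients out of the window before they die. For those patients, 24-hour notice then depends on a judgement of relatedness, which is the filter that 6.2 leaves out for deaths on infusion.

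**Working it through.** No sample size, power or event figure underlies this point, so there is no plan figure to reproduce. The check traces each stated route by which a death could reach the SMC, and asks whether it applies once esmolol is off and the death is judged unrelated.

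| Route | Section | Condition | Death after a stop, judged unrelated |
|---|---|---|---|
| 24-hour death report | 6.2 | Esmolol running | Not covered |
| 24-hour SAE alert | 10.2, Appendix 4 | Serious and related | Not covered |
| 24-hour unanticipated-problem report | A4.1 | Unexpected, at least possibly related, and suggesting greater risk | Not covered |
| 7-day report | Appendix 4 | Unexpected and study related | Not covered |
| Relatedness assessment sent to the SMC | 10.1 | Event judged reportable | Possible, no deadline stated |
| Permanent STOP event reported as an adverse event | 10.1 | Permanent discontinuation | Possible, no deadline stated |
| Scheduled review | 6.2, Appendix 4 | 3 and 6 enrolled | Covered if a review is still to come |
| Access to study data and narratives | 6.2 | None | Available, but not a notification |

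**Illustration (times assumed).** Shock worsens at 10:00, esmolol is stopped, and the patient dies at 10:45. The death comes 45 minutes after the stop. It is inside the 24-hour window of section 10.2 and outside the window of section 6.2.

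**How such a death is likely to be classified.** Section 10.1 attributes a STOP event to the underlying sepsis if it persists more than 20 minutes after discontinuation. A4.3 exempts cardiogenic shock that has not resolved 20 minutes after cessation. In the illustration, 45 minutes exceeds 20 minutes. These rules concern STOP events and shock, not death as such, but they favour judging the death that follows as unrelated.

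**Conflict between A4.3 and 10.2.** Death is a serious adverse event under section 10.2 and is collected to 24 hours after infusion whatever its cause. A4.3 exempts unrelated deaths from adverse event reporting and states no time window. The same death in the illustration is collected under one section and may be exempt under the other.

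**Scheduled reviews.** Planned enrolment is up to 10 and the last stated review is at 6. So 10 − 6 = 4 patients, or 4/10 = 40%, enter after it. This counts patients, not expected deaths; the documents give no figure for deaths after a STOP event.

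**The case against.** The case for leaving the text alone has substance.

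- **Other routes exist.** Reportable events go to the SMC with a relatedness assessment, and permanent STOP events are reported in their own right. The SMC has the data and patient narratives. Appendix 4 has the principal investigator consult the SMC chair on whether a serious event could be drug-caused.
- **The A4.3 exemption is limited.** Its heading says only that outcomes may be exempt, and it does not apply to events judged related or of uncertain relationship. Under A4.2 the probably/possibly grade is available when one or more of the criteria for a definite relationship are absent, which is a low bar.
- **The window has a rationale.** Section 8.1 says the effects of esmolol reverse within minutes of stopping, and section 10.1 treats them as gone by 20 minutes.
- **Some material cannot be seen.** The A4.4 decision tree and part of the list of events always treated as drug-related are missing from the text available for review.

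These points defeat three stronger readings that a reader might infer. The first is that the 6.2 safeguard is practically empty. It still covers sudden death before any STOP criterion, and death after the infusion has restarted following a heart-rate hold or an approved resumption. The second is that the investigator's opinion decides whether the SMC ever hears of a death. It bears on the 24-hour clock, not on all knowledge. The third is that such a death has no dated route at all. That cannot be asserted with the decision tree unseen, and a scheduled review may still lie ahead.

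The core is unaffected. Access is not notification, and the routes open to an unrelated death carry no 24-hour deadline. Even a death graded uncertain is not plainly within an alert worded for related events. The short-action rationale assumes that a collapse begun on esmolol reverses with the drug, which is what case review would examine.

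**Conclusion.** The point holds in a limited form. The all-cause 24-hour death report stops at the end of infusion, while the protocol's own serious-event window runs 24 hours longer. A death in that gap that is judged unrelated has no guaranteed 24-hour notice to the SMC in the visible text. Separately, A4.3 and section 10.2 disagree about unrelated deaths in the same 24 hours and must be reconciled.

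The reach is small in absolute terms: at most 10 patients, with 4 entering after the last stated review. How many deaths would fall in the gap is unknown. The conclusion assumes that the unseen A4.4 tree does not already require 24-hour notice of such deaths; if it does, 6.2 and A4.3 still need aligning with it. Whether these are the deaths that matter most is a judgement and is not needed here. This is a should-fix item: a cheap improvement to safety oversight, not a defect that invalidates the study.

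**What to change.** In section 6.2, replace the limit to deaths on infusion with: every death from the first esmolol infusion through 24 hours after the last esmolol infusion (the section 10.2 window), whatever the attributed cause and whether or not the infusion had been stopped. Counting from first to last infusion also settles deaths during a temporary hold.

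In A4.3, state that the exemption does not apply to deaths in that window. Check the A4.4 decision tree and align it if needed.

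The cost is a sentence in each of two sections, possibly a change to one figure, and a few more narratives among at most 10 patients. The change affects reporting only and leaves dosing, STOP rules and clinical care as they are.
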